8.8 Safety Analyses

Safety assessment analyses for this study will include summaries of unsolicited adverse events, concomitant medications, suicidal ideation and behavior, and vital signs. Qualitative safety analyses will examine safety data with summary tables listing drug exposure, concomitant medications/therapies, unsolicited AEs, and percentages tabulated overall and by group.

8.8.1 Analysis of Exposure

The frequencies and percentages of participants with exposure will be summarized overall and by dose group. Data will be tabulated for the *mITT* Set.

8.8.2 Analysis of Adverse Events

The primary measure of safety will be the reporting of unsolicited AEs. All AEs collected from Enrollment to Termination will be categorized as follows:

- Pretreatment AEs are defined as AEs that occur during the Preparatory Period prior to the first dose in the first Experimental Session
- Treatment Emergent AEs are defined as AEs that occur during the Treatment Period from the first Experimental Session to the last Integrative Session
- AEs that occur on and two days after MDMA or placebo administration
- AESIs are defined as AEs specified in the protocol related to cardiac function and abuse liability
- Follow-up Period AEs are defined as AEs that occur during the Follow-up Period after the last Integrative Session through Termination
- AEs leading to discontinuation of IP
- AEs resulting in death or hospitalization.
- SAEs
- AEs continuing at Termination.

Verbatim terms on case report forms will be mapped to preferred terms (PT) and system organ class (SOC) using the Medical Dictionary for Regulatory Activities (MedDRA) Version 17.0. Frequency and incidence of AEs will be displayed by PT, sorted by SOC, and summarized by treatment group, analysis set, category (as defined above), severity, and seriousness. AEs will be analyzed and presented as follows:

- If a participant has more than one AE mapped to the same PT, that AE will be reported once using the highest severity
- Relationship will be determined based on relative incidence of TEAEs with at least two-fold difference between MDMA vs. placebo
- Compare relative incidence of AEs during Experimental Sessions such as clinical signs and symptoms, such as chest pain, shortness of breath, or neurological symptoms or any other signs or symptoms that may be indicative of a medical complication of the investigational product
- AEs that occur on day of Experimental Sessions and two days after IP administration will be presented separately.

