10.1.2 PTSD, Suicide Risk, and Psychotherapy

During Screening, throughout MDMA-assisted psychotherapy, and during assessment of study measures, participants will be asked to think about and discuss their thoughts and emotions relating to the traumatic event or events. They may experience intense emotional responses or suicidal ideation as a result of recalling and speaking about this material. Even in a therapeutic context, thinking about and discussing the trauma, symptoms related to the trauma or the effects

of PTSD on life function can produce distress and exacerbate suicidal ideation during and immediately after psychotherapy sessions. Psychotherapy is conducted as part of this study, and people undergoing psychotherapy are expected to confront unpleasant thoughts, feelings and memories in the process. Because psychotherapy is an integral part of the research study design, the potential distress arising from psychotherapy is unavoidable. Therapy teams will provide emotional support to participants during any psychological distress.

The therapy team will minimize risks by carefully evaluating all participants to determine if there is a current risk of suicidal behavior. Participants with a history of suicide attempts will not be excluded unless significant risk of suicidal ideation and/or behavior is detected, per Exclusion Criteria described in [Section 4.2](#). Participants will be enrolled according to the Eligibility Criteria based on the clinical judgment of the site physician, therapy team, and Medical Monitor.

A qualified individual will administer the C-SSRS according to [Table 6: Time and Events-Study Measures](#), and as needed depending on clinical presentation of the participants, to monitor for development and intensity of suicidal ideation and/or behavior. The therapy team will implement the following plan to assess elevated or imminent suicide risk.

If the Since Last Visit C-SSRS reveals current serious Suicidal Ideation (scores of four or greater), indicating risk at the time of the assessment, or positive Suicidal Behavior (scores of one or greater), the participant will be referred for further management as described below.

1. If the participant has current suicidal ideation, but no specific plan to commit suicide (Suicidal Ideation Score=4), the individual administering the C-SSRS will ensure:

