 - a. The participant is evaluated by the investigator and/or site physician to determine an appropriate course of action. Findings will be discussed with the participant and their personal therapist, if applicable.
 - b. Regular check-ins via phone or in-person will be continued until the participant has stabilized or a new course of action is taken based on changes in C-SSRS score and/or ongoing clinical assessment.
 - c. Notification of the sponsor within 24 hours of this event and provide a narrative for the AE for expedited reporting to FDA. Increases in suicidality will be captured as an AESI per [Section 11.1.1](#) and evaluated for seriousness. SAEs will be reported per regulatory guidance.
 - d. Treatment would be continued when deemed appropriate by the investigator and Medical Monitor, unless it is determined that treatment should be discontinued, in which case the participant will enter follow-up.
2. If the participant has suicidal ideation, and a plan to commit suicide (Suicidal Ideation Score=5) or positive Suicidal Behavior (Score greater than or equal to 1), the individual administering the C-SSRS will assess whether the risk is imminent. A Suicidal Ideation score of five does not necessarily indicate an immediate risk if the thoughts are fleeting, fairly easily controlled, and deterrents are strong. If there is no imminent risk, the individual will follow the procedure described above. If there is imminent risk of suicidal behavior, the individual will ensure:
 - a. Participants are evaluated by the investigator or site physician to determine an appropriate course of action, and the therapy team will contact their personal therapist, who will be invited to come to the study site to assist, depending on their location.
 - b. If it is determined that the participant is at imminent risk of suicide, the therapy team will do one of the following:
 - i. Escort the participant to the ED (Emergency Department);

- ii. Escort the participant to an appropriate mental health services facility (e.g., hospital psychiatric unit); or
- iii. Call EMS (Emergency Medical Services) and ensure that the participant is transferred to the responding medical personnel.
- c. If the participant will not comply and wishes to leave without consultation, call EMS. Explain that the participant is in immediate danger of committing suicide. Provide a complete description of the participant and give any other needed details to ensure the participant's safety.

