- d. Notification of appropriate members of the study team and sponsor representatives within 24 hours, provide a narrative for the AE for expedited reporting to FDA.
- e. The event will be collected as an AESI per [Section 11.1.1](#) and seriousness will be evaluated. SAEs will be reported per regulatory guidance.
- f. Treatment would be continued when deemed appropriate by the investigator and Medical Monitor, unless it is determined that treatment should be discontinued, in which case the participant will enter follow-up.

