11.1.1 Adverse Events of Special Interest

In accordance with guidance for the specific study site, Health Canada Clinical Safety Data Management Definitions and Standards for Expedited Reporting ICH Topic E2A: Guidance for Industry or FDA Safety Reporting Requirements for INDs and BA/BE Studies, the sponsor will

pay special attention to a subset of AEs involving cardiac function that could be indicative of QT interval prolongation or cardiac arrhythmias, including *Torsade de pointes*, sudden death, ventricular extrasystoles, ventricular tachycardia, ventricular fibrillation and flutter, non-postural syncope, and seizures. The subset of AEs involving suicide risk under the following terms are also of special interest: suicides, suicide attempts, self-injurious behavior associated with suicidal ideation, and suicidal ideation judged to be serious or severe in the opinion of the investigator. These AEs will be marked in the eCRF with the denotation “Adverse Event of Special Interest” (AESIs) whether serious or non-serious.

In order to assess signals of abuse potential for the IMP in the intended patient population:

- AESIs involving the terms of Behavioral addiction, Drug abuser, Substance abuser, Dependence, Intentional product misuse, Overdose (accidental, intentional, or prescribed), or Drug diversion in cases that are related to MDMA or “Ecstasy” (material represented as MDMA) will be collected and coded as AESIs in the eCRF.
- Cases of noncompliance, protocol violations, participants lost to follow-up, and any other reasons why participants dropped out of the study will be assessed for presence of AESIs.
- Qualitative urine drug test data will be collected prior to each Experimental Session. Any positive findings that cannot be attributed to pre-approved concomitant medications or diet will be reviewed by the Medical Monitor to assess compliance with ongoing eligibility criteria and for presence of AESIs.

If an AESI is a SAE (Serious Adverse Event) or if it involves suicide risk, it should be reported to the sponsor with a narrative via the eCRF within 24 hours of the site’s awareness of the event.

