3.3 Safety Objectives

The overall safety objective is to assess differences between groups in severity, incidence and frequency of Adverse Events (AEs), Treatment Emergent AEs (TEAEs), AEs of Special Interest (AESIs), and Serious Adverse Events (SAEs), concomitant medication use, suicidal ideation and behavior, and vital signs to support the package insert for MDMA-assisted psychotherapy. The following safety objectives will evaluate the safety of MDMA-assisted psychotherapy compared to identical psychotherapy with inactive placebo:

1. Compare relative incidence of AEs during Experimental Sessions that may be indicative of a medical complication of the Investigational Product (IP) such as clinical signs and

- symptoms of chest pain, shortness of breath, or neurological symptoms or any other signs or symptoms that prompt additional vital sign measurements.
2. Compare relative incidence of AEs by severity.
 3. Compare relative incidence of TEAEs, to determine relationship to the IP based on relative incidence in the MDMA group.
 4. Compare relative incidence of TEAEs by severity reported during an Experimental Session, 1 and 2 days after IP administration.
 5. Compare relative incidence of AESIs, defined as AEs specified in the protocol related to cardiac function and abuse liability.
 6. Compare relative incidence of AEs by severity categorized as leading to discontinuation of IP, resulting in death or hospitalization, and continuing at Termination
 7. Compare relative incidence of SAEs
 8. Compare relative incidence of concomitant medications taken during an Experimental Session, 1 and 2 days after IP administration.
 9. Compare relative incidence of psychiatric concomitant medications taken during the Treatment Period.
 10. Compare relative incidence of positive or serious ideation and suicidal behavior assessed with the Columbia Suicide Severity Rating Scale (C-SSRS) by treatment group.
 11. Compare mean changes in blood pressure, heart rate, and body temperature from pre-IP administration to end of each Experimental Session by treatment group.

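### The AESI comparison is limited to cardiac and abuse-related events, so it leaves out the suicide-risk events that Protocol 11.1.1 also makes AESIs

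*SAP*

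**What the plan says.** **Where AESIs are defined for collection.** Protocol 11.1.1 starts with cardiac events and then adds: "The subset of AEs involving suicide risk under the following terms are also of special interest". The terms it lists are suicides, suicide attempts, self-injury linked to suicidal ideation, and "suicidal ideation judged to be serious or severe in the opinion of the investigator". It then gives the abuse-potential terms. Sites flag AESIs in the eCRF whether or not they are serious. An AESI that involves suicide risk must reach the sponsor with a narrative within 24 hours even when it is non-serious.

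Protocol 10.1.2 applies this to the C-SSRS. Its management plan starts when the scale "reveals current serious Suicidal Ideation (scores of four or greater), indicating risk at the time of the assessment, or positive Suicidal Behavior". For an ideation score of 4 it says "Increases in suicidality will be captured as an AESI per" Section 11.1.1. For a score of 5 or suicidal behavior with imminent risk it says "The event will be collected as an AESI per" Section 11.1.1. Without imminent risk, the score-4 procedure applies.

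**Where AESIs are defined for analysis.** SAP 8.8.2 says "AESIs are defined as AEs specified in the protocol related to cardiac function and abuse liability". SAP 3.3, objective 5, reads "Compare relative incidence of AESIs, defined as AEs specified in the protocol related to cardiac function and abuse liability". Objective 5 in Protocol 3.3 and in the synopsis has the same content.

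**What else covers suicidality.** Safety objective 10 and SAP 8.8.4 compare C-SSRS ideation and behavior by arm. SAP 8.8.2 also displays all AEs by preferred term and system organ class, by arm, severity and seriousness, with separate SAE and death-or-hospitalization categories.

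**The concern.** The two definitions do not match. One of the three groups that sites are told to mark as AESIs is outside the AESI comparison as the analysis sections define it. The mismatch lies within the protocol (synopsis and Section 3.3 against 10.1.2 and 11.1.1) as well as between protocol and SAP.

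The stated purpose of the safety comparison is to support the package insert. An AESI summary built to SAP 8.8.2 would not agree with the AESI flags in the database. The missing group is one to which the protocol gives expedited handling. The programmer would have to choose between the flag and the SAP sentence with no rule to decide.

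**Working it through.** The main point is a comparison of texts. The plan states no figure to reproduce.

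**Step 1. Set the definitions side by side.**

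| Place | Cardiac | Suicide risk | Abuse |
|---|---|---|---|
| Protocol 11.1.1 | yes | yes | yes |
| Protocol 10.1.2 (suicidality only) | – | yes | – |
| Synopsis, objective 5 | yes | no | yes |
| Protocol 3.3, objective 5 | yes | no | yes |
| SAP 3.3, objective 5 | yes | no | yes |
| SAP 8.8.2 | yes | no | yes |

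Four of four analysis statements list 2 groups. The collection section lists 3. The missing group in each case is suicide risk.

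**Step 2. Follow one event.** A participant scores 4 on C-SSRS ideation at an Integrative Session, and the event is non-serious. Under 10.1.2 and 11.1.1 the site marks an AESI and reports it within 24 hours. Under SAP 8.8.2 the event is neither cardiac nor abuse-related, so it does not enter the AESI category. It does appear under its preferred term and system organ class by arm, and the response counts as serious ideation in the SAP 8.8.4 table.

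**Step 3. Ask whether the other displays supply the same count.** The cut-offs in SAP 8.8.4 (ideation 4 or 5, or any behavior) largely match the trigger in 10.1.2, so the overlap is large. The unit differs, however. SAP 8.8.4 counts positive scale responses by time period. Protocol 11.1.1 concerns eCRF-marked events, including self-injury linked to ideation and ideation that the investigator judges serious or severe. The preferred-term display counts a participant once per term, so a participant can appear under several terms. Adding those rows does not give the number of participants with any suicide-risk AESI.

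**Step 4. A separate, optional check on the two-fold rule in SAP 8.8.2.** That rule determines relationship from an incidence ratio of at least 2. It does not say what happens when placebo has no events. The documents give no AE rates, so I assume 50 per arm (the planned mITT size) and equal true incidence p in both arms. The probability that the ratio is undefined is

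P(placebo 0, MDMA ≥ 1) = (1 − p)^50 × [1 − (1 − p)^50].

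At p = 2% this is 0.364 × 0.636 = 0.232. Exact enumeration of the two binomials gives the chance of a flag with no true difference:

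| True incidence, both arms | Zero-placebo terms not counted | Zero-placebo terms counted |
|---|---|---|
| 1% | 2.7% | 26.6% |
| 2% | 10.2% | 33.3% |
| 4% | 20.3% | 31.6% |
| 10% | 16.6% | 17.2% |

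For rare terms the unstated convention changes the result materially. By 10% incidence it hardly matters.

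**The case against.** **The SAP wording may already import Protocol 11.1.1.** It refers to events specified in the protocol. That is fair as far as it goes, but the same sentence then limits the set to two groups. At best it is ambiguous.

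**The exclusion may be deliberate, since suicidality has its own objective.** This is possible, but neither document says so, and 10.1.2 and 11.1.1 call these events AESIs without qualification. A deliberate exclusion would need one sentence.

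**The events are visible anyway.** This largely stands and sets the size of the point. A reader might infer that suicide-risk events drop out of the safety comparison, or that the AESI table would pass for evidence that none occurred. The documents do not support either. Such events stay in the AE displays by arm and, where they qualify, in the SAE and death-or-hospitalization categories. Objective 10 puts the C-SSRS comparison beside them. What is missing is the AESI grouping and its count.

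**Telephone C-SSRS results.** A reader might also infer that these go untabulated, because SAP 8.8.4 does not name telephone contacts among its time periods. But the time-and-events tables in both documents tick telephone follow-up at Visits 6, 11 and 16, which are Integrative Sessions, and SAP 8.8.4 names that period. A clarifying phrase would help. There is no sign of lost data.

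**The two-fold rule.** A reader might treat it as a second error, since a ratio of 2 cannot be reached once observed placebo incidence exceeds 50%. SAP 8.0, however, sets a general chi-square approach for nominal variables. By exact enumeration at 50 per arm, for assumed rates of 80% against 50%, the two-fold rule flags 10.6%. A chi-square excess on MDMA and a Newcombe interval above zero each flag 89.5%. Whether SAP 8.0 reaches individual preferred terms is unclear, so this calls for clarification. The missing zero-placebo convention is a plain omission, but a minor one.

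**Conclusion.** The AESI comparison is wrong as written. All four statements of it cover two of the three groups that Protocol 11.1.1 defines, and taken literally they exclude the suicide-risk AESIs that sites record. This follows from the text and needs no assumption.

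The consequence is limited to the AESI category and its between-arm summary. Data collection, the general AE and SAE reporting and the C-SSRS comparison are unaffected. The number of events involved cannot be derived from the documents.

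The correction should be made before the safety tables are programmed, because it is nearly free and removes a contradiction in both documents. The points on telephone C-SSRS results and the two-fold rule are optional clarifications. The rates shown for the two-fold rule depend on the assumed incidences and on 50 per arm.

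**What to change.** **Required.** Replace the two-group wording with the Protocol 11.1.1 definition in the synopsis (objective 5), Protocol 3.3 (objective 5), SAP 3.3 (objective 5) and SAP 8.8.2. In SAP 8.8.2, tabulate AESIs by arm under three groups (cardiac function, suicide risk, abuse liability) and print zero counts. The cost is wording edits in four places and one extra table group. The eCRF flag already exists, so no new data are needed.

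**Optional clarifications.**
- In SAP 8.8.4, state that telephone C-SSRS results are tabulated with the Integrative Session period under which the calls are scheduled.
- In SAP 8.8.2, state how terms with no placebo events are treated under the two-fold rule, and show the risk difference with its 95% confidence interval beside the incidences.
- State whether the general chi-square approach in SAP 8.0 applies to individual preferred terms.
- Keep any change in how relationship is described consistent with Protocol 11.1. That section determines relationship by analysis and does not collect investigator opinion except for SAEs.

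These cost a few sentences and three table columns (the difference and its two limits). Displaying the interval does not reduce chance flagging of rare terms by the two-fold rule, but it does show how uncertain each flag is.

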8.8.3 Concomitant Medications

A secondary measure of safety will be the reporting of concomitant medications. All concomitant medications collected from Screening to Study Termination will be categorized as follows:

- Pretreatment medications are defined as medications taken prior to and after signing informed consent and those taken during the Preparatory Period prior to the first Experimental Session. A stop date is expected prior to the first Experimental Session for any medications requiring a change in dose, a skipped dose, or tapering.
- Treatment Period concomitant medications are defined as those taken or continued during the Treatment Period from the first Experimental Session to the last Integrative Session. A stop date is expected prior to the each Experimental Session for any medications requiring a change in dose, a skipped dose, or tapering.
- Concomitant medications with a start date of the day of and two days after IP administration
- Follow-up Period concomitant medications are defined as those taken or continued during the Follow-up Period after the last Integrative Session through Termination
- Any concomitant medications that are tapered
- Any concomitant medications that are taken to treat an AE
- Any concomitant medications that are taken to treat an SAE
- Any excluded concomitant medications taken as a deviation from the protocol.

Concomitant medications on case report forms will be classified using the WHO Drug Dictionary Enhanced™ (WHO DDE). Frequency and incidence of concomitant medications will be displayed by generic name, sorted by class, and summarized by treatment group, analysis set, and category as defined above. Concomitant medications will be analyzed and presented as follows:

- Concomitant medications taken on the day of and two days after IP administration will be presented separately
- Any psychiatric concomitant medications by period.

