1. Compare relative incidence of AEs during Experimental Sessions that may be indicative of a medical complication of the Investigational Medicinal Product (IMP), such as clinical signs and symptoms of chest pain, shortness of breath, or neurological symptoms or any other signs or symptoms that prompt additional vital sign measurements.
2. Compare relative incidence of AEs by severity.
3. Compare relative incidence of TEAEs, to determine relationship to the IMP based on relative incidence in the MDMA group.
4. Compare relative incidence of TEAEs by severity reported during an Experimental Session, 1 day, and 2 days after IMP administration.
5. Compare relative incidence of AESIs, defined as AEs specified in the protocol related to cardiac function and abuse liability.
6. Compare relative incidence of AEs by severity categorized as leading to discontinuation of IMP, resulting in death or hospitalization, and continuing at Study Termination.
7. Compare relative incidence of SAEs.
8. Compare relative incidence of psychiatric concomitant medications taken during an Experimental Session, 1 day, and 2 days after IMP administration.
9. Compare relative incidence of any psychiatric concomitant medications taken during the Treatment Period.
10. Compare relative incidence of positive or serious suicidal ideation and positive suicidal behavior assessed with the Columbia Suicide Severity Rating Scale (C-SSRS) by treatment group.
11. Compare mean changes in blood pressure, heart rate, and body temperature from pre-IMP administration to end of each Experimental Session by treatment group.

Recruitment and Participant Population

Approximately N≈100 participants with a confirmed diagnosis of at least severe PTSD will be enrolled. Participants will be recruited through print and internet advertisements, referrals from other treatment providers, and by word of mouth. The sponsor will monitor demographics on an ongoing basis and encourage diversity (representative of PTSD population) in enrollment of study participants by communicating with sites. Randomization will be stratified by clinical site.

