3.3 Safety Objectives

The overall safety objective is to assess differences between groups in severity, incidence and frequency of Adverse Events (AEs), Treatment Emergent AEs (TEAEs), AEs of Special Interest (AESIs), and Serious Adverse Events (SAEs), concomitant medication use, suicidal ideation and behavior, and vital signs to support the package insert for MDMA-assisted psychotherapy. The following safety objectives will evaluate the safety of MDMA-assisted psychotherapy compared to identical psychotherapy with inactive placebo:

1. Compare relative incidence of AEs during Experimental Sessions that may be indicative of a medical complication of the Investigational Medicinal Product (IMP) such as clinical signs and symptoms of chest pain, shortness of breath, or neurological symptoms or any other signs or symptoms that prompt additional vital sign measurements.
2. Compare relative incidence of AEs by severity.
3. Compare relative incidence of TEAEs, to determine relationship to the IMP based on relative incidence in the MDMA group.
4. Compare relative incidence of TEAEs by severity reported during an Experimental Session, 1 day, and 2 days after IMP administration.
5. Compare relative incidence of AESIs, defined as AEs specified in the protocol related to cardiac function and abuse liability.
6. Compare relative incidence of AEs by severity categorized as leading to discontinuation of IMP, resulting in death or hospitalization, and continuing at Study Termination.
7. Compare relative incidence of SAEs.
8. Compare relative incidence of concomitant medications taken during an Experimental Session, 1 day, and 2 days after IMP administration.
9. Compare relative incidence of psychiatric concomitant medications taken during the Treatment Period.
10. Compare relative incidence of positive or serious suicidal ideation and positive suicidal behavior assessed with the Columbia Suicide Severity Rating Scale (C-SSRS) by treatment group.
11. Compare mean changes in blood pressure, heart rate, and body temperature from pre-IMP administration to end of each Experimental Session by treatment group.

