14.2.2 Safety Analyses

Safety analyses will confirm safety data with summary tables listing exposure to IMP, unsolicited AEs, concomitant medications, suicidal ideation and behavior, and vital signs overall and by group. If a participant has more than one AE mapped to the same PT, that AE will be reported once using the highest severity. AEs that occur on Day 0 (Experimental Session), Day 1, Day 2 after IMP administration will be presented separately. Compare relative incidence of AEs during Experimental Sessions such as clinical signs and symptoms, such as chest pain, shortness of breath, or neurological symptoms or any other signs or symptoms that may be indicative of a medical complication of the IMP.

Frequency and incidence of concomitant medications will be displayed by generic name, sorted by class, and summarized by treatment group, analysis set, and category. Concomitant medications taken on Day 0 (Experimental Session), Day 1, Day 2 after IMP administration will be presented separately. Any psychiatric concomitant medications will be tabulated by period (Preparatory, Treatment Period, Follow-up Period). Frequency and incidence of positive or serious ideation and suicidal behavior will be presented using descriptive statistics of C-SSRS scores in tabular format. Vital signs (heart rate, blood pressure, and body temperature) for Experimental Sessions will be summarized using descriptive statistics in tabular format listing values at pre-IMP administration, prior to the supplemental dose, and at the end of each Experimental Session by treatment group. Additional details are available in the Statistical Analysis Plan.

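### SAP 8.8.3 defines dosing-window medications by start date, while the objective and every other statement define them by use; under the start-date rule, repeat use on one continuing record is missed at later sessions

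*SAP*

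**What the plan says.** SAP 8.8.3 lists categories of concomitant medication. The one for the dosing window reads "Concomitant medications with a start date of the day of and two days after IP administration". The section then says that summaries are "summarized by treatment group, analysis set, and category as defined above", so this category drives a table. Under its presentation rules, the same section states: "Concomitant medications taken on the day of and two days after IP administration will be presented separately".

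The objective behind the table is item 8 of SAP 3.3: "Compare relative incidence of concomitant medications taken during an Experimental Session, 1 and 2 days after IP administration". Item 8 of Protocol 3.3 matches it: "Compare relative incidence of concomitant medications taken during an Experimental Session, 1 day, and 2 days after IMP administration". Protocol 14.2.2 says "Concomitant medications taken on Day 0 (Experimental Session), Day 1, Day 2 after IMP administration will be presented separately". The protocol synopsis also speaks of use, but limits the item to psychiatric drugs: "Compare relative incidence of psychiatric concomitant medications taken during an Experimental Session, 1 day, and 2 days after IMP administration".

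The neighbouring SAP category is use-based as well: "Treatment Period concomitant medications are defined as those taken or continued during the Treatment Period". The Follow-up Period category is built the same way.

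**The concern.** A start date records when a drug was first begun. Objective 8 asks which drugs were used around dosing. The two coincide for a drug taken once. They part for a drug prescribed once and taken as needed, and the protocol foresees such use: 10.2.2.2, 10.2.4.1 and 12.2 provide for occasional benzodiazepines or sleep aids for distress and insomnia after sessions.

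A programmer who follows 8.8.3 must choose between its two lines. If the start-date line is chosen, repeat use after Sessions 2 and 3 can drop out of the table. Those are the sessions at which the protocol allows the higher initial dose. The comparison is a named between-group safety objective, meant to support the package insert, so the rule should be fixed before unblinding.

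**Working it through.** The plan gives no figure to reproduce, so the check sets the definitions side by side and then traces how one drug is counted under each.

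**Definitions.** Six statements describe the window: the category line and the presentation line of SAP 8.8.3, item 8 of SAP 3.3, item 8 of Protocol 3.3, item 8 of the protocol synopsis, and Protocol 14.2.2. Five say taken. Only the SAP category line says start date.

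**Counting rules.** Each session window is Day 0 to Day 2, three days. Protocol 8.3.1 puts sessions at least 21 days apart, so windows cannot overlap and one start date falls in at most one of them. For one record:
- count by start date = 1 if the start date lies in a window, otherwise 0;
- count by use = number of windows with at least one intake.

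**Trace (assumed patterns of use).**

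| Pattern | By start date | By use | Windows missed |
|---|---|---|---|
| (a) One open record, started on Day 0 of Session 1, taken on Day 0 of all three sessions | 1 of 3 | 3 of 3 | 3 − 1 = 2 |
| (b) Same use, but a new record each time, or the record closed before each session and reopened | 3 of 3 | 3 of 3 | 0 |
| (c) One open record, started on Day 5 after Session 1, taken in the windows of Sessions 2 and 3 | 0 of 2 | 2 of 2 | 2 − 0 = 2 |

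Neither document says whether the table is by session. If each participant is counted once across sessions, (a) gives 1 under both rules and loses nothing. Pattern (c) gives 0 against 1, so that participant is still lost.

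**Direction between arms.** Assume that 20% of the MDMA arm and 10% of the placebo arm start an as-needed drug in the Session 1 window on one open record, and average the three session rates. These rates are illustrative; the documents give none. By start date, the averages are (20+0+0)/3 = 6.7% and (10+0+0)/3 = 3.3%, ratio 2, whatever happens later. By use:
- both arms repeat at every session: 20% v 10%, ratio 2, unchanged, although the difference is 10 points rather than 3.3;
- only the MDMA arm repeats: 20% v 10/3 = 3.3%, ratio 6, so the start-date rule understates the contrast;
- only the placebo arm repeats: 20/3 = 6.7% v 10%, ratio 0.67, so the start-date rule shifts it the other way.

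**Partial dates.** SAP 8.2.1 sets an unknown start day to the first-dose day when month and year match. Unless the section's allowance for a more conservative date is used, a start-date rule would place such a drug in the Session 1 window whenever in that month it was actually begun.

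**The case against.** The strongest reply is that nothing need be lost. The presentation line of 8.8.3 already counts by use, and five of the six statements agree on the intended meaning. The recording conventions may also generate new start dates. SAP 8.8.3 expects a stop date before each session for drugs that need a dose change, a skipped dose or tapering. Protocol 4.3 and 12.3 require most prescription drugs to be withheld before each session (one week in one section, five half-lives in the other, which itself needs reconciling). Protocol 12.1 collects discontinuations and additions. A drug withheld and restarted could therefore follow pattern (b), where the rules agree. Even otherwise, it would still appear under the Treatment Period category and, where applicable, among drugs taken to treat an AE and psychiatric drugs by period.

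Much of this stands. A reader might infer that as-needed drugs first prescribed after Session 1 are simply not counted at Sessions 2 and 3. The documents do not support that: it needs both the start-date line to prevail and the drug to stay on one continuing entry, and neither is stated. A reader might also infer a bias toward no difference between arms. That is not shown either; the relative incidence is unchanged if repeat use is alike in both arms.

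What the reply does not remove is the conflict. The SAP contains a stated rule that does not measure its objective and ties its tables to that rule. Whether an as-needed drug that was merely not taken meets the stop-date convention is unclear.

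**Conclusion.** The inconsistency is established from the text. Its effect is conditional: up to two of three windows are missed for a participant who starts a drug in the Session 1 window and uses it after every session, and every window is missed for a drug first started outside any window. Both results assume that the start-date line governs and that there is one continuing record. The first also assumes a by-session table. The loss is zero if each use has its own record.

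The documents give no rates of repeat use by arm, so neither the size nor the direction of any effect on the between-arm comparison can be stated. The effect is limited to one table within what SAP 8.8.3 calls a secondary measure of safety, for which that section names no test. The primary and key secondary analyses, alpha and power are untouched. This is a modest correction worth making before unblinding.

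**What to change.** In SAP 8.8.3, replace the start-date wording of the dosing-window category with use. A medication counts in a session's Day 0 to 2 window if a recorded intake falls in it or, for a scheduled drug, if its start-stop interval overlaps it. Show drugs ongoing and unchanged since before Session 1 on a separate line, so that background medication does not blur the contrast. State whether the table is by session or counts each participant once. State how as-needed use is dated on the eCRF. At the same time, settle whether objective 8 covers all medications or, as in the synopsis, psychiatric ones only.

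The cost is SAP wording and a programming change, with one limit. Protocol 8.3.2 and 8.3.3 have teams ask about medication use at calls and Integrative Sessions, but do not say that each intake is dated. Without intake dates, an as-needed drug can be classified only by its record interval, which may overcount: a drug begun on Day 5 after Session 1, taken only after Session 2 and left open past Session 3 would count in 2 windows instead of 1. Flag such entries in the table.
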